#### **D. Statistical Analysis Plan**

For categorical variables, counts and percentages will be presented. As a check on randomization, groups will be compared using the Fisher's exact test. For continuous variables, mean, median, standard deviation (SD) and inter-quartile range (IQR) will be presented. Groups will be compared using the t-test, except that non-parametric methods will be used for variables distributed non-symmetrically.

##### **D1. Aim 1:**

Each SEFAS response has 5 ordinal response choices scored 0 through 4. With 12 items and with the lowest score (0) representing the most severe disability, the total score ranges from 0 to 48. If a subject omits one or more questions, the total score will be re-normalized to 48. Group differences in the SEFAS scores at the 12 month time point will be analyzed using the t-test or Mann-Whitney test, as appropriate.

Patients who are withdrawn from the study due to failure of the initial nerve block will be considered as screening failures; no follow-up data or questionnaire scores will be obtained. The same approach will be taken for patients who decide to withdraw from the study, or are withdrawn by the attending surgeon or anesthesiologist, after randomization but before the single shot nerve block procedure.

Patients lost to follow-up after the end of the 5 day nerve block will be analyzed with a per-protocol analysis. We consider that, since the follow-up begins after the end of the treatment and consists only of completing questionnaires, there is unlikely to be a bias towards the experimental or control group having drop-outs.

Patients who have to (or choose to) remove the pump before the entire 5 day treatment period will be analyzed both an intent-to-treat analysis and a per-protocol analysis. The duration of pump use will be noted.

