Randomization: We will use a block-stratified randomization schedule with blocks of sizes 2 and 4. The West Chester and Uptown locations will have separate randomization schedules as it is thought the two locations provide somewhat different populations, making it desirable to have approximately equal numbers in the control and experimental groups at each site. Due to the requirement for quarantine of the ropivacaine prepared by IDS, subject randomization may sometimes deviate from the schedule: a subject scheduled to receive a pump may be placed in the control group if no ropivacaine is available at the time of their surgery, which will be compensated by placing a subsequent subject scheduled to be in the control group into the experimental group when drug is available. These deviations will not be based on subject characteristics, so that assignments remain random, and the total number of control and experimental subjects at each site will remain the same.

Data collection: We will establish an online copy of the SEFAS which subjects can use to enter their responses. This will be done using the REDCap (Research Electronic Data Capture) system for secure web based capture of questionnaire data. For patients opting to have a link to the SEFAS sent to their cell phones, the REDCap-Twillio integration platform will be used. Patients electing not to use the online entry format will be contacted by the research nurse via the preferred route indicated on the consent form, and the research nurse will then enter the data into the Redcap project database. Data from the questionnaires will be exported out of REDCap to be merged with the data from the Medidata Rave® database for analysis. All other data will be entered directly into the Medidata Rave® clinical database. Clinical demographic data will be obtained from the patient at the beginning of the study and verified with the electronic medical record. Analgesic use in the perioperative period will be obtained from the electronic medical chart. Patients typically receive acetaminophen and celecoxib preoperatively, then opioids postoperatively as needed. However, participating in the study will not affect the subjects' options for treatment for pain. Numerical pain ratings recorded in the PACU will be obtained from the electronic medical chart. The Verbal Numerical Scale (VNRS, 0 = no pain, 5 = moderate pain, 10 = worst possible pain) is used for patients in the

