 A single serious adverse event of LAST requiring rescue medication, cardiac resuscitation, or transfer to the ICU.

During the 5 day period of ambulatory pump use:

 A single serious adverse event of catheter site infection requiring hospital admission.

 A single serious adverse event of LAST requiring hospital admission.

During the entire study period:

 A single serious adverse event of any life-threatening adverse event deemed possibly related to the use of the ropivacaine pump.

 Two subjects receiving pumps experiencing moderate adverse events of tinnitus and/or metallic taste in the mouth.

11. Data Safety monitoring plan and/or DSMB:

As discussed in section 6, the medical monitor, [name], will review subject's research data and adverse events to ensure patient safety.”

12. Data Analysis:

The primary outcome measure is SEFAS scores at the indicated time points. A secondary outcome measure is use of opioids in the immediate postoperative period.

Each SEFAS response has 5 ordinal response choices scored 0 through 4, with the lowest score (0) representing the most severe disability and the highest total score being 48. If subjects omit a question the score will be re-normalized; however, the Redcap interface will be designed to try to obtain an answer for each question. The Mann-Whitney test will be used to examine differences in the SEFAS scores at each time point. For analysis of SEFAS scores, the pilot study sample size of 20 per group is sufficient for detecting a difference in scores between groups of 9 points with a power of 0.8 and $\alpha = 0.05$ (using the standard deviation obtained from SEFAS use in an ankle surgery study[35]); this score would represent moving up one rank in 3/4 of the questions which would be a functionally meaningful improvement given the 0 – 4 ordinal scale employed. . Patients who are withdrawn from the study due to failure of the initial nerve block (see above) will be considered as screening failures; no follow-up data or questionnaire scores will be obtained. We consider that such a failure is unlikely to have any relationship to the chronic pain outcome we are studying. The same approach will be taken for patients who decide to withdraw from the study, or are withdrawn by the attending surgeon or anesthesiologist, after randomization but before the single shot nerve block procedure.

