## **B. Specific Aims and Hypotheses**

Aim 1: Test the hypothesis that SEFAS scores at the one year time point are higher (better outcome) in subjects who received a ropivacaine pump compared to patients who received standard care. This is the primary outcome measure).

Aim 2: Test the hypothesis that SEFAS scores at earlier time points (14 day, 3 month, 6 month) are higher in subjects who received a ropivacaine pump compared to patients who received standard care.

Aim 3: Test the hypothesis that pain scores and total opioid use in the PACU are lower in subjects receiving the ropivacaine pump.

Aim 4: Conduct a preliminary examination of possible roles of confounding clinical and demographic variables, focusing on: severity of ankle fracture; sex; and body mass index (BMI).

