##### **D2. Aim 2:**

Group differences in the SEFAS scores will be analyzed using a t-test or Mann-Whitney test at the 14 day, 3, and 6 month time points...

D2. Aim 3:

The times the patient enters and is discharged from the PACU will be recorded. Discharge from the PACU is based on several criteria, one of which is adequate pain control. Hence duration of PACU stay is relevant to pain experienced by the subject but there may be non-pain related reasons for prolonging the PACU stay. Verbal pain scores on a scale of 0 (least painful) to 10 (worst pain imaginable) are recorded periodically by the nursing staff and entered into the chart; the timing of these entries cannot be expected to be completely uniform and patients with higher pain may be queried more often. Pain scores will therefore be summarized by an area-under-the curve analysis, using a score of 3 as a reference value. A simple average of all pain ratings captured in the PACU will also be examined. Both sets of values will be compared between experimental and control groups using the t-test or Mann-Whitney test, as appropriate.

Time and amount of opioid medications will be captured from the PACU record. Different opioid drugs will be converted into analgesic equivalents using the values presented at <http://www.globalrph.com/narcotic.htm>. Total equivalent opioid use will be compared between experimental and control groups using the t-test or Mann-Whitney test.

D4. Aim 4:

Demographic and clinical data will be compared between the groups to determine if values differ significantly despite randomization (table \*\*\* below). A preliminary analysis of possible confounding clinical variables that may influence the development of chronic pain will be conducted. Linear regression analysis will be used to examine the contributions of these 3 variables and the treatment group (experimental or control) to the SEFAS score at 12 months. It is expected that this small pilot study will lack the power to fully analyze confounders, but the analysis may be used to guide future, larger studies.

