## I. Mock tables to be produced

Table 1: Descriptive table of demographics of experimental and control groups prior to intervention.

Description	Control (N = ***) 	Experimental (N = ***) 	p value
Age at ankle surgery (years)			
Weight at time of surgery			
Height at time of surgery			
BMI at time of surgery			
Race			
Ethnicity			
Ankle fracture: number of malleoli affected			
Grade of injury (defined as closed injury, or open injury with Gustilo Anderson classification grade 1, grade 2, grade 3a, grade 3b, grade 3cr) 			
Time in surgery			
Estimated blood lost in surgery			
Number of plates implanted			
Total length of plates implanted			
Total number of screw holes in implanted hardware			

Mean, SD, median, interquartile range for continuous variables, number and % per group for categorical variables.

 Converted to ordinal scale 1 – 6

Table 2 Pain outcomes

Description	Control (N = ***)	Experimental (N = ***)	p value
Opioid medication use in PACU: analgesic equivalents			
Time in PACU			
PACU discharge status (home, rehab facility, hospital) 			
PACU Pain score AUC			

Average Pain score in PACU			
SEFAS score (2 week)			
Pain medication use analgesic equivalents (2 week)			
SEFAS score (3 month)			
Pain medication use analgesic equivalents (3 month)			
SEFAS score (6 month)			
Pain medication use analgesic equivalents (6 month)			
SEFAS score (12 month)			
Pain medication use analgesic equivalents (12 month)			
Number (%) with any chronic pain diagnosis at 12 months			

 Converted to ordinal scale 1 – 3

Table 3 Other outcomes

Description	Control (N = ***)	Experimental (N = ***)	p value
Number (%) requiring re-operation			
Number (%) : Indication for re-operation (infection, non-union, hardware failure, hardware removal, other)			
Wound healing status at first FU (dehiscence, cellulitis , deep infection, healing well, other) 			
Wound healing status at second FU (dehiscence, cellulitis , deep infection, healing well, other) 			
Weight bearing current status at first FU [full, assisted (cane, walker, boot), non (crutch)] 			
Weight bearing current status at second FU [full, assisted			

(cane, walker, boot), non (crutch)] 			
---	--	--	--

 Converted to ordinal scale

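### Randomisation is stratified by location, but location is in no SAP analysis or variable list, so the 12-month SEFAS test is conservative and gives up power if the sites differ

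*SAP*

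**What the plan says.** Under Randomization in section 7, the protocol sets up permuted blocks of 2 and 4 and explains the stratification: "The West Chester and Uptown locations will have separate randomization schedules as it is thought the two locations provide somewhat different populations". Subjects may be swapped between arms when drug is unavailable, but the arm totals at each site are to be preserved.

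SAP section D1 gives the primary comparison: "Group differences in the SEFAS scores at the 12 month time point will be analyzed using the t-test or Mann-Whitney test, as appropriate". The earlier SEFAS time points (Aim 2) are handled the same way.

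The only model with covariates is in SAP section D4: "Linear regression analysis will be used to examine the contributions of these 3 variables and the treatment group". SAP section B identifies the three variables as fracture severity, sex and BMI.

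Location is not in the analysis data set (SAP section E), the derived variables (section F) or mock Table 1 in section I, described as a "Descriptive table of demographics of experimental and control groups prior to intervention". SAP section C calls the study single-center and does not mention the two locations.

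On power, protocol section 12 states that "the pilot study sample size of 20 per group is sufficient for detecting a difference in scores between groups of 9 points", at power 0.8 and alpha 0.05. The SD comes from a cited study and is not given as a number. The same section names one test: "The Mann-Whitney test will be used to examine differences in the SEFAS scores at each time point". The SAP's general rule (section D) differs: "Groups will be compared using the t-test, except that non-parametric methods will be used for variables distributed non-symmetrically".

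**The concern.** Stratified randomisation balances the arms within each site. That makes the treatment difference less variable when site predicts outcome. A two-group test without site does not use this: its standard error still includes the between-site variance. The test then rejects less often than 5% under the null, and its interval is wider than the design requires.

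Two further things are at stake:

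- **Pilot value.** SAP section D4 says the confounder analysis may guide larger studies. With site outside the data set, the pilot cannot report how prognostic site is or show that the arms were balanced by site.
- **Choice of primary test.** The protocol fixes Mann-Whitney, whereas the SAP allows either test depending on the distribution. In an open-label trial that choice should not be left until the data are seen. Naming one site-adjusted analysis settles both matters.

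**Working it through.** **Inputs from the documents.** 20 per arm, 9-point difference, alpha 0.05, power 0.8 (protocol section 12); 60 enrolled for 40 evaluable (protocol section 6); blocks of 2 and 4 within site (protocol section 7).

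**Assumptions.** Two-sided test; site gaps of 0, 4.5 and 9 SEFAS points; site splits of 20/20 or 30/10; normal scores.

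**Step 1: the plan's power figure.** With no numeric SD the figure cannot be reproduced directly, so it is inverted. For a t-test with 38 degrees of freedom, the noncentrality is 9 / (SD × √(2/20)). Power 0.80 requires SD = 9.90, since 9 / (9.90 × 0.3162) = 2.87. The normal approximation gives 10.16, and Mann-Whitney (relative efficiency 0.955) gives 9.66. The stated power is therefore consistent with an SD of about 9.7 to 10.2.

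**Step 2: what site adjustment removes.** Hold the total SD at 9.9 and let p be the share of subjects at one site. Then within-site SD = √(9.9² − gap² × p(1 − p)). With p = 0.5:

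- Gap 4.5: √(98.01 − 5.06) = 9.64.
- Gap 9: √(98.01 − 20.25) = 8.82, a ratio of 8.82 / 9.9 = 0.89, or an 11% smaller standard error.

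**Step 3: simulation, total SD 9.9, sites 20/20, arms balanced within site, 40,000 runs per cell.**

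| | Gap 0 | Gap 4.5 | Gap 9 |
|---|---|---|---|
| Null rejection, t-test | 0.048 | 0.043 | 0.028 |
| Null rejection, regression with site | 0.049 | 0.049 | 0.051 |
| Null rejection, Mann-Whitney | 0.047 | 0.043 | 0.028 |
| Null rejection, van Elteren | 0.048 | 0.050 | 0.051 |
| Power, t-test | 0.801 | 0.802 | 0.827 |
| Power, regression with site | 0.801 | 0.818 | 0.884 |
| Power, Mann-Whitney | 0.777 | 0.780 | 0.795 |
| Power, van Elteren | 0.768 | 0.789 | 0.857 |
| 95% CI half-width, t-test | 6.30 | 6.31 | 6.33 |
| 95% CI half-width, with site | 6.30 | 6.14 | 5.61 |

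With a 30/10 split, t-test null rejection is 0.049, 0.046 and 0.033. Power without and with site is 0.797 vs 0.797, 0.806 vs 0.817 and 0.818 vs 0.862.

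**Step 4: the other reading of the SD.** If 9.9 is the within-site SD, the total SD grows with the gap and unadjusted power falls. With blocks of 2 and 4 and a 50:50 split (5,000 null and 3,000 effect runs per cell):

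| Site gap | t-test null rejection | Power, t-test | Power, with site |
|---|---|---|---|
| 0 | 0.049 | 0.79 | 0.79 |
| 3 | 0.047 | 0.79 | 0.79 |
| 5 | 0.045 | 0.78 | 0.80 |
| 9 | 0.035 | 0.74 | 0.80 |
| 12 | 0.023 | 0.69 | 0.80 |

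On either reading, adjustment gains about 6 power points at a 9-point gap and 1 to 2 points at a gap of 4.5 to 5.

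**Step 5: attrition.** With 60 randomised, random loss to 40 and total SD 9.9, t-test null rejection is 0.046 at gap 4.5 and 0.034 at gap 9. Power is 0.80 vs 0.81 and 0.81 vs 0.88. At gap 0, adjustment costs under 1 power point.

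**Step 6: a supportive repeated-measures model.** If k subjects per arm have a 6-month but no 12-month score, in addition to 20 with both, the variance of a 12-month mean falls by the fraction r² × k / (20 + k). Both r and k are assumed. For k = 3: 0.25 × 3/23 = 3.3% at r = 0.5 and 0.64 × 3/23 = 8.3% at r = 0.8. For k = 5: 5.0% and 12.8%. Subjects withdrawn at or before the block give no scores, so they add nothing.

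**The case against.** The strongest objection is size. The protocol says only that the populations are thought to differ somewhat, not that SEFAS differs. At a 4.5-point gap the gain is under 2 power points and 6.31 − 6.14 = 0.17 points of half-width on a 0–48 scale. The striking figures need a site gap as large as the treatment effect the trial is powered for. This stands: the benefit is small unless the gap is large.

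Second, the conservatism depends on balance within site among those analysed, and removals after randomisation and loss to follow-up weaken it. This stands in part. Step 5 shows the alpha figures moving closer to 0.05, while the power gain remains.

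Third, 40 subjects cannot estimate a site effect well: with 20 per site and SD 9.9, its interval is about ±6.3 points. That is fair, but a wide estimate is still more use for planning than none.

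Fourth, the simulations use normal scores, whereas SEFAS is bounded and may be skewed. This also stands, and is why a rank counterpart should be named in advance.

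Finally, the test discrepancy and the repeated-measures model do not follow from omitting site. They are secondary, and the case for adjustment does not depend on them.

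**Conclusion.** The concern holds. Location determines the randomisation schedules and appears in no SAP test, regression, variable list or mock table. The consequence is lost efficiency and a reporting gap, not bias: type I error is not inflated, and the stated power is not contradicted.

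The size is conditional on assumed site gaps and splits and a back-solved SD. It is nil at gap 0, minor at about 5 points or less, and about 6 power points with an 11% narrower interval at 9 points when the sites are of equal size. The linear adjustment has no measurable cost when the arms are balanced within site and site is irrelevant, and costs under 1 power point after random attrition. The change should be made, though the trial remains interpretable without it.

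**What to change.** 1. Add randomisation site to SAP section E and to mock Table 1.
2. Make the primary 12-month analysis a pre-specified linear regression of SEFAS on treatment and site, reporting the adjusted difference with its 95% CI. Name the van Elteren test, stratified by site, as the non-parametric counterpart. Report it in all cases, so that the choice between them does not depend on the data.
3. Add site to the Aim 4 regression.
4. Amend protocol section 12 so that both documents name the same test.
5. As a supportive analysis only, fit a repeated-measures model to SEFAS at 14 days, 3, 6 and 12 months with treatment, visit, treatment-by-visit and site. State that it assumes data missing at random and so does not resolve loss driven by pain.

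The cost is redrafting, one variable already known for every subject, and a little more analysis in SAS 9.4, which SAP section H already names. Site uses one degree of freedom. The van Elteren test loses about 1 power point against Mann-Whitney if site is irrelevant (0.768 vs 0.777).

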changes in medical practice that may reduce development of chronic pain conditions after trauma and surgery.

6. Study design:

This is an investigator-initiated, single-center, prospective, non-blinded, randomized pilot study. We are requesting authorization to enroll up to 60 patients to allow for 40 evaluable subjects.

Adults undergoing surgery for open reduction and internal fixation for traumatic ankle fracture will be invited to participate in the study comparing the 2 forms of nerve block. All patients are currently given the option of popliteal nerve block (single injection of ropivacaine given just prior to surgery), which helps provide pain relief in the immediate postoperative period; the surgery itself is done under general anesthesia. Participants who have agreed to have the single shot procedure will be randomized into the control group (standard-of-care single injection of local anesthetic just prior to surgery) or experimental group (standard-of-care single injection plus 5 day ambulatory popliteal nerve block).

Standard-of care procedures for placement of the popliteal nerve block are as follows: The blocks are performed in the Same Day Surgery (Pre Op Holding Area), by Anesthesia Residents with direct supervision by Anesthesia Attending Faculty. All residents performing blocks are at training level PGY2 (second year resident) or above. Monitors utilized for block placement will be EKG, SpO₂, and Non Invasive Blood Pressure monitor. Standard ASA monitors are on the patient for the block. Supplemental oxygen is in every room as needed. A Code Cart is readily available in SDS and PACU for resuscitative measures if needed (rescue medications, ACLS Medication). A Lipid rescue agent (20% Intralipid solution) is available at all times in the OR Pharmacy (right next to Same Day Surgery). A difficult airway cart is available in PACU and SDS as well for any need for managing the airway. If there is a minor vascular injury (inadvertent needle puncture of the artery) the needle is repositioned prior to the injection. The single injection for popliteal nerve block generally consists of 20 ml of 0.5% ropivacaine. As part of standard care, patients sign a separate clinical consent form specifically for lower limb nerve block procedures.

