**E. Variables in the analysis data set with Definitions**

Description
Patient unique ID
Age at ankle surgery
Date of ankle surgery
Weight and height at time of surgery
Date of enrollment
Gender
Race
Ethnicity
Randomized to control or experimental group?
Ankle fracture: number of malleoli affected
Grade of injury (defined as :closed injury, or open injury with Gustilo Anderson classification grade 1, grade 2, grade 3a, grade 3b, grade 3cr)
Opioid medication use in PACU: time, agent, dose, and route for each administration
Times entered and discharged from PACU
PACU discharge status (home, rehab facility, hospital, AMA)
Verbal pain scores in PACU (0 – 10 scale) and times at which recorded
Surgical Hardware: number of plates implanted, length and number of screw holes of each.
Estimated blood loss during surgery
Pain medication prescription at discharge (drug, dose)
Start time of surgery
End time of surgery
SEFAS score (2 week, 3, 6, 12 month post surgery)
Subject-reported analgesic use (2 week, 3, 6, 12 month post surgery)
Dates of post-surgical follow-ups (FU)
Weight bearing recommendation at each FU (non, partial, full, other)
Weight bearing current status at each FU [full, assisted (cane, walker, boot), non (crutch)]
Pain status at each FU (none, mild, severe)
Pain medication prescriptions at each FU (drug, dose)
Wound healing status at each FU (dehiscence, cellulitis , deep infection, healing well, other)
Range of motion at each FU
Re-operation required?
Date of re-operation

Indication for re-operation (infection, non-union, hardware failure, hardware removal, other)
Chronic pain conditions diagnosed at one year FU.

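### The 12-month SEFAS comparison uses only patients who answer at 12 months; the drop-out argument covers how many are lost, not who is lost, and the earlier scores are left out of that contrast

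*SAP*

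**What the plan says.** The primary analysis in SAP D1 is a single-visit test: "Group differences in the SEFAS scores at the 12 month time point will be analyzed using the t-test or Mann-Whitney test, as appropriate". Earlier scores are compared separately under Aim 2, "using a t-test or Mann-Whitney test at the 14 day, 3, and 6 month time points", and mock Table 2 reports each visit on its own line.

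Loss to follow-up is covered by one sentence, "Patients lost to follow-up after the end of the 5 day nerve block will be analyzed with a per-protocol analysis", with matching text in Protocol section 12. The reason offered is the timing and nature of the follow-up: "since the follow-up begins after the end of the treatment and consists only of completing questionnaires". From this the SAP infers that "there is unlikely to be a bias towards the experimental or control group having drop-outs". The Protocol's wording makes explicit that this refers to the number of drop-outs in each arm.

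Early pump removal is treated differently: "Patients who have to (or choose to) remove the pump before the entire 5 day treatment period will be analyzed both an intent-to-treat analysis" (the sentence goes on to name a per-protocol one as well). Neither document names an imputation method, a longitudinal model or a missing-data sensitivity analysis. Protocol section 12 adds that estimating drop-out is one purpose of the pilot.

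**The concern.** A patient who completed treatment and later missed a questionnaire has not departed from the assigned treatment, so the per-protocol label does not say how that patient is to be analysed. In practice, a two-sample test on 12-month scores without imputation can use only the scores observed at 12 months.

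The defence of this rests on similar drop-out counts. Bias depends on whether the patients who leave differ in outcome from those who stay, and whether that difference varies by arm. Patients know their treatment, the outcome is their own report of pain and function, and follow-up lasts a year, so outcome-related loss that differs by arm is plausible. At stake are the accuracy of the 12-month difference that would inform a full-sized study, and some precision in a trial planned around 20 evaluable patients per arm.

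**Working it through.** **1. What a partly followed patient contributes.** Take a patient with SEFAS at 14 days, 3 and 6 months and none at 12 months. Under Aim 2 the patient enters three tests. Under Aim 1 the patient enters none. The earlier scores are used in the trial, but not in the primary contrast.

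**2. An SD to work with.** The Protocol gives 20 per group, a 9-point difference, power 0.8 and alpha 0.05, but no SD, so its figure cannot be reproduced directly. Back-solving the two-sided normal formula gives SD = 9 / [(1.960 + 0.842) × √(2/20)] = 9 / (2.802 × 0.3162) = 10.16. The noncentral t version gives 9.90. An SD of about 9.9 is therefore consistent with the plan, and it is an assumption.

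**3. Why equal counts are not enough.** Let ρ be the correlation between an earlier score and the 12-month score. Let s be the amount, in SD units, by which completers' mean earlier score exceeds that of everyone in their arm. If loss depends only on the earlier score:

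completer bias = ρ × SD × (s in pump arm − s in control arm)

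The number lost does not appear on its own. Equal s in both arms gives no bias; unequal s gives bias even with equal counts. As a check, a simulation with SD 10, one third missing and low scorers lost in controls only corresponds to s of about 0.4 in controls and 0 with the pump. The formula gives 9 − 0.5 × 10 × 0.4 = 7.0, 9 − 0.7 × 10 × 0.4 = 6.2 and 9 − 0.8 × 10 × 0.4 = 5.8. The simulated values were 7.0, 6.2 and 5.8.

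**4. Range of results.** Assumptions: 30 per arm, SD 9.9, true difference 9, about 30% missing, ρ 0.6 to 0.8.

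| What loss at 12 months depends on | Completers only | Using earlier scores | Completer bias |
|---|---|---|---|
| Nothing, or standing within own arm in the same way in both arms | about 9.0 | 9.0 | none |
| Absolute earlier score, both arms (falls mainly on controls) | 7.3 to 7.8 | 9.0 | −1.7 to −1.2 |
| Earlier score in controls only; random with pump | 6.3 to 7.3 | 9.0 | −2.7 to −1.7 |
| The 12-month score itself, controls only | about 5.7 | 6.8 to 7.7 | about −3.3 |

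The spread in the third row reflects the correlation and how strongly loss depends on the score. The runs giving 6.8 to 7.3 had about 30% missing in both arms, so bias arose with equal losses. A deliberately extreme case makes the same point: low scorers lost in controls, high scorers lost with the pump, about 19.2 retained in each arm (SD 10, one third missing, ρ 0.5 to 0.8). There completers gave 4.3 to 6.1.

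**5. Precision.** Under random loss of a fraction f, using the earlier score multiplies the standard error by √(1 − f × ρ²). With f = 0.3 this is √(1 − 0.3 × 0.36) = 0.944 at ρ = 0.6 and √(1 − 0.3 × 0.64) = 0.899 at ρ = 0.8, a reduction of 6% to 10%. Under selective control loss the simulated standard errors fell from 3.08 to 2.96 (4%) at ρ = 0.6 and from 3.09 to 2.77 (10%) at ρ = 0.8. These gains assume that drop-outs were seen at earlier visits; patients lost soon after surgery carry less information.

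**The case against.** The plan does argue its case. Follow-up is questionnaires only, begins after treatment ends, uses the patient's preferred contact route and is paid per questionnaire, all of which should limit loss. If loss is random, or depends in the same way on standing within each arm, the completer test is unbiased. This is also a pilot that sets out to measure drop-out, and a mixed model is only one of several adequate methods. All of that stands. It limits the expected size of the problem and argues against insisting on one model. It does not show that loss is unrelated to outcome.

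Two stronger readings are tempting and should be resisted.

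- A reader might take the plan to "enroll up to 60 patients to allow for 40 evaluable subjects" as a forecast that one third will be lost to follow-up. The gap, 1 − 40/60 = 33%, is not tied to any cause. It may include failed blocks and withdrawals before the block, which both documents treat as screening failures with no questionnaires obtained. One third is at most a ceiling, and no analysis recovers patients who have no scores.
- A reader might infer that the earlier scores are discarded altogether. They are tested under Aim 2 and tabulated; they are absent only from the 12-month contrast.

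**Conclusion.** The point holds in limited form. The plan defines no analysis set for patients lost to follow-up, its primary test can use only observed 12-month scores, and its reason for expecting no bias is insufficient because it speaks to numbers lost rather than to who is lost.

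Under the stated assumptions the size runs from no bias to about −1 to −3 points on a true difference of 9. In the scenarios tabulated the error is toward the null; a different pattern of loss could reverse it. The SD is back-solved, and the missing fraction, correlations and drop-out mechanisms are assumed, so these are illustrations and not predictions for this trial.

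Using earlier scores corrects only loss that those scores explain. If loss depends on the unseen 12-month score, part of the bias stays: 6.8 to 7.7 against a true 9. This is worth changing because the data are already collected, although the precision gain alone is modest.

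**What to change.** For the 12-month contrast in SAP D1:

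- Analyse, by assigned arm, all randomised patients with at least one SEFAS, using a method that draws on the earlier scores. Examples are a repeated-measures mixed model with arm, visit, arm-by-visit and site, or multiple imputation from the earlier scores.
- Keep the completers-only t-test or Mann-Whitney test as a sensitivity analysis.
- Add a simple delta-shift sensitivity analysis for loss that depends on unobserved outcome.
- Report drop-out by arm and visit, with reasons, separating screening failures from later loss.
- Replace the per-protocol sentence with this definition, and delete the statement that bias is unlikely in both documents.

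The cost is SAP and Protocol wording and a little more analysis, with no new visits or data; SAS 9.4 is already listed in SAP section H. The main analysis then assumes approximate normality and that loss is explained by observed data. The completers' rank test does not check the second assumption, because it faces the same missing scores; the delta-shift analysis is there to show how far the result depends on it.
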